NCT03438266

Study ID: 1650-801-008

Title: A Multicenter, Single-blind, Randomized, Controlled Study of the Safety and Effectiveness of JUVÉDERM VOLUMA® XC Injectable Gel for Cheek Augmentation Using Cannula

Protocol Date: 19 October 2017

ALLERGAN – CONFIDENTIAL

The following contains confidential, proprietary information which is the property of Allergan

Study Title: A multicenter, single-blind, randomized, controlled study of the safety and effectiveness of JUVÉDERM VOLUMA[®] XC injectable gel for cheek augmentation using cannula

Protocol Number: 1650-801-008

Product Name: JUVÉDERM VOLUMA[®] XC injectable gel

Development Phase: Post-market

Sponsor: Allergan
[name]

Manufacturer: Allergan

Safety reporting: [REDACTED]
[REDACTED]

Names and contact information of Allergan study personnel are provided in the supplementary Study Contacts page.

Approval Date: 19-Oct-2017

INVESTIGATOR SIGNATURE PAGE

Study Title: A multicenter, single-blind, randomized, controlled study of the safety and effectiveness of JUVÉDERM VOLUMA® XC injectable gel for cheek augmentation using cannula

Protocol Number: 1650-801-008

Product Name: JUVÉDERM VOLUMA® XC injectable gel

Investigator:

Study Location:

I agree to:

- Implement and conduct this study diligently and in strict compliance with this protocol, good clinical practices (GCP), and all applicable laws and regulations.
- Maintain all information supplied by Allergan in confidence and, when this information is submitted to an Institutional Review Board (IRB), Ethics Committee (EC), or another group, it will be submitted with a designation that the material is confidential.

I have read this protocol in its entirety and I agree to all aspects.

Investigator Printed Name

Signature

Date

Approval Date: 19-Oct-2017

RETURN TO ALLERGAN

Synopsis

NUMBER AND TITLE OF STUDY: 1650-801-008: A multicenter, single-blind, randomized, controlled study of the safety and effectiveness of JUVÉDERM VOLUMA® XC injectable gel for cheek augmentation using cannula

DEVELOPMENT PHASE: Postmarket

STUDY CENTERS: Up to 7 United States sites

NUMBER OF SUBJECTS: Up to 75 subjects will be enrolled in order to have 60 subjects treated

OBJECTIVES: The objective of this study is to evaluate the safety and effectiveness of JUVÉDERM VOLUMA XC (hereafter VOLUMA XC) injectable gel using cannula in subjects seeking correction of age-related volume deficit in the mid-face.


STUDY DESIGN: This is a multicenter, evaluator-blind, randomized, within-subject controlled, paired-comparison study of the safety and effectiveness of VOLUMA XC injectable gel using a cannula and needle for cheek augmentation to correct age-related volume deficit in the mid-face.
 
At screening, after written informed consent has been obtained, the Treating Investigator (TI) will document the subject's demographics, Fitzpatrick skin phototype, height, weight, vital signs, and medical, surgical, cosmetic, and dental procedures history. Female subjects of childbearing potential will undergo urine pregnancy testing. All subjects will complete the validated 5-item Satisfaction with Cheeks module of the FACE-Q questionnaire. The blinded Evaluating Investigator (EI) will rate the subject's mid-face deficit for the overall mid-face area, [REDACTED] on the validated 6-point photonumeric Mid-Face Volume Deficit Scale (MFVDS) (0 = none, 1 = minimal, 2 = mild, 3 = moderate, 4 = significant, 5 = severe) to determine eligibility for the study.
 
On the randomization/treatment day, subjects will have 1 cheek treated with VOLUMA XC injectable gel using a [REDACTED] cannula and the contralateral cheek treated using a [REDACTED] with a goal to achieve at least a 1-grade improvement. In the cheek randomized for cannula use, a maximum treatment with cannula should be attempted. [REDACTED]
 
[REDACTED] The side of treatment (ie, side of face for needle or cannula) will be randomized. The left side of face will be treated first for all subjects. For the cheek treated with cannula, an anesthetic agent must be used on the treatment area prior to making the entry point with the introductory needle; use of anesthesia is optional for the cheek treated with needle only. The TI will inject VOLUMA XC in the mid-face to correct mid-face volume deficit. [REDACTED]
 
[REDACTED]
 
At 1 and 3 months after treatment, subjects will return for a visit during which the EI will rate subjects on the MFVDS for the overall mid-face area, [REDACTED] the TI will record any adverse events (AEs), and subjects will complete the Satisfaction with Cheeks module of the FACE-Q questionnaire. Subjects will be exited from the study at the end of the Month 3 visit.


DIAGNOSIS AND CRITERIA FOR INCLUSION/EXCLUSION: Adults with age-related volume deficit in the mid-face who are seeking to increase facial volume in the mid-face.
 
INCLUSION:
 
 1. 35 to 65 (inclusive) years of age and in good general health 2. Has overall mid-face severity of Moderate (3) for both cheeks, Significant (4) for both cheeks, or Severe (5) for both cheeks on the 6-point photonumeric MFVDS as assessed by the EI 
[REDACTED]

Approval Date: 19-Oct-2017

EXCLUSION:

[REDACTED]

8. Has experienced trauma to the mid-face area within 6 months before enrollment or has residual deficiencies, deformities, or scarring

[REDACTED]

10. Has a history of anaphylaxis or allergy to lidocaine (or any amide-based anesthetics), HA products, or Streptococcal protein, or is planning to undergo allergen desensitization therapy during the term of the study

11. Has active autoimmune disease

12. Has current cutaneous or mucosal inflammatory or infectious processes (eg, acne, herpes, gum disease), abscess, an unhealed wound, or a cancerous or precancerous lesion, above the subnasale

[REDACTED]

TEST PRODUCT, DEVICE VOLUME, AND MODE OF ADMINISTRATION:

VOLUMA[®] XC (a hyaluronic acid injectable gel with lidocaine) will be administered via [REDACTED] cannula and [REDACTED] needle to the mid-face to correct mid-face volume deficit. Appropriate injection volume for the mid-face will be determined by the T[REDACTED]

DURATION OF STUDY: Treatment period: 1 day. Follow-up period: 3 months

Approval Date: 19-Oct-2017

RESPONSE MEASURES:

Effectiveness: The primary effectiveness measure is the blinded EI’s assessment of the subject’s overall mid-face volume deficit for each cheek on the MFVDS. The timepoint for the primary effectiveness endpoint is Month 1. The secondary effectiveness measure is the FACE-Q Satisfaction with Cheeks questionnaire evaluated by the subject.

Safety: Safety measures include the presence and severity of injection site responses (ISRs), which will be recorded by the subject in the subject diary for 30 days after treatment, procedural pain assessments, and any adverse events (AEs). Location of these assessments will be noted as being on the right and/or left cheek or not applicable.

STATISTICAL METHODS:

[REDACTED]

Effectiveness analyses: For the primary effectiveness analysis of change from baseline (screening) to Month 1 in overall mid-face MFVDS, the mean paired difference between treatment with cannula and treatment with needle and its 95% CI based on paired t-test will be calculated. If the upper confidence limit is < 0.5, statistical non-inferiority will be concluded.

[REDACTED]

[REDACTED]

[REDACTED]

Safety analyses: ISRs, procedural pain assessment, and AEs will be summarized using descriptive statistics. ISRs and, separately, AEs will be summarized by the percentage (and 95% CI) of subjects who have the ISR (or AE) on both sides, by the percentage (and 95% CI) of subjects who have the ISR (or AE) on the cannula side and not on the needle side, and by the percentage (and 95% CI) of subjects who have the ISR (or AE) on the needle side and not on the cannula side. Also, the within-treatment percentage (and 95% CI) of subjects who have the ISR (or AE) will be summarized for the cannula side and, separately, for the needle side.

Approval Date: 19-Oct-2017

Table of Contents

Synopsis 3

Table of Contents 6

List of Tables 9

List of Figures 9

1. Abbreviations and Terms 11

█ [REDACTED]

█ [REDACTED]

█ [REDACTED]

2.3 Clinical Rationale 13

3. Study Objectives and Clinical Hypotheses 13

3.1 Study Objectives 13

3.2 Clinical Hypotheses 14

4. Study Design 14

4.1 Structure 14

4.2 Duration 14

4.3 Treatment Groups and Treatment Regimen 14

4.3.1 Study Treatment 14

4.3.2 Control Treatment 14

4.3.3 Methods for Blinding 14

4.4 Permissible and Prohibited Medications/Treatments 15

4.4.1 Permissible Medications/Treatments 15

4.4.2 Prohibited Medications/Treatments 15

4.4.3 Special Diet or Activities 16

4.5 Treatment Allocation Ratio and Stratification 16

5. Study Population 16

5.1 Number of Subjects 16

5.2 Study Population Characteristics 16

5.3 Inclusion Criteria 17

5.4 Exclusion Criteria 17

█ [REDACTED]

█ [REDACTED]

Approval Date: 19-Oct-2017

9.1.2	Instructions for Use and Administration	30
9.1.3	Treatment Regimen Adjustments	31
9.2	Other Study Supplies	31
10.	Study Administration Procedures	31
10.1	Subject Entry Procedures	31
10.1.1	Overview of Entry Procedures	31
10.1.2	Informed Consent and Subject Privacy	32
10.1.3	Method for Assignment to Treatment Groups	32
10.2	Compliance with Protocol	33
10.3	Pregnancy	33
10.4	Study Termination	33
11.	Adverse Events	34
11.1	Definitions	35
11.1.1	Adverse Event	35
11.1.2	Serious Adverse Event	36

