8.3.4 Safety Analyses

ISRs, procedural pain assessment, and AEs will be summarized using descriptive statistics. The primary safety analysis of ISRs and AEs will be summarized by the percentage (and 95% CI) of subjects who have the ISR (or AE) on both sides, by the percentage (and 95% CI) of subjects who have the ISR (or AE) on the cannula side and not on the needle side, and by the percentage (and 95% CI) of subjects who have the ISR (or AE) on the needle side and not on the cannula side. Also, the within-treatment percentage (and 95% CI) of subjects who have the ISR (or AE) will be summarized for the cannula side and, separately, for the needle side.

ISRs reported by subjects will be summarized by symptom, maximum reported severity, maximum reported duration (ie, calendar days from first occurrence to last reported occurrence during the 30-day ISR period), and number of ISR days (ie, calendar days with non-zero severity, after accounting for days with missing reports during the ISR duration). Adverse events will be summarized by System Organ Class and Preferred Term, and will be tabulated by duration, severity, causality, action taken, relationship to treatment, and outcome. The summary will include incidence rate as well as total number of events. AEs that occur before treatment will be listed, but not summarized.

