10.4 Study Termination

If conditions arise during the study that indicate that the study or an investigational site needs to be terminated, Allergan, the TI, monitor, IRB, and/or regulatory agencies will discuss the situation and take appropriate action after consultation. Conditions that may warrant termination of the study or site include, but are not limited to:

- the discovery of an unexpected, serious, or unacceptable risk to subjects enrolled in the study
- the decision on the part of Allergan to suspend or discontinue testing, evaluation, or development of the study device
- failure of the TI to comply with pertinent national or state regulations, IRB-imposed conditions, or protocol requirements

- TI submission of knowingly false information to Allergan, a study monitor, the IRB, or any regulatory agency

Per International Organization for Standardization (ISO) 14155, if a study is prematurely terminated or suspended due to safety issues, Allergan shall inform all Investigators and the regulatory authorities of the termination or suspension and the reason(s) for the termination or suspension. The IRB is also to be informed promptly and provided the reason(s) for the termination or suspension by Allergan or by the Investigator, as specified by the applicable regulatory requirements. If a premature termination or suspension occurs, Allergan shall remain responsible for providing resources to fulfill the protocol obligations and existing agreements for follow-up of subjects enrolled in the study, and each Investigator or authorized designee shall promptly inform enrolled subjects, if applicable.

11. Adverse Events

Throughout the course of the study, all AEs will be monitored and reported on an AE eCRF, including seriousness, severity, action taken and relationship to study treatment. If AEs occur, the first concern will be the safety of the study subjects.

Although the risk of developing a serious complication is small, the TI and the research staff will monitor each subject closely, and, if a complication occurs, they will use their medical judgment to do whatever is necessary to treat the problem. If subjects have any ongoing treatment-related AE at the time of the final visit, they must continue to be followed up until resolution of these events or the subject condition is considered stable by the TI. After the final visit, the subject will resume receiving the standard medical care according to the standard care of the clinic.

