- swelling or edema around the eye following an injection can result in a temporary decrease of vision.
- in rare circumstances, facial fillers have been associated with granulomas, which are small inflammatory nodules under the skin.

Unforeseeable risks or results are also a possibility. The risk of developing a serious complication is small. If a complication occurs, subjects will be advised to contact the TI who will use his/her medical judgment to do whatever is necessary to treat the subject.

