4.2 Study Objectives and Endpoints

The objective of this study is to evaluate the safety and effectiveness of VOLUMA XC injectable gel using cannula in subjects seeking correction of age-related volume deficit in the mid-face.

The study primary objective, secondary objective, and other objectives are presented with corresponding endpoint(s) below:

Table 4-1 Study Objectives and Corresponding Endpoints

Objectives	Endpoints	
To evaluate the safety and effectiveness of cannula versus needle for the correction of age-related volume deficit in the mid-face.	Primary Endpoint: • MFVDS response distribution by treatment, based on EI assessment on a 6-point scale of ordinal categories, from 0 to 5 (none, minimal, mild, moderate, significant, severe), for baseline and change from baseline to month 1 (primary endpoint)	
	 MFVDS responder rates by treatment, based on EI assessments on a 6-point scale of ordinal categories, from 0-5 (none, minimal, mild, moderate, significant, severe), with responders defined as ≥1 grade improvement from baseline, for month 1 (primary measurement time) Subject's FACE-Q Satisfaction with Cheeks, at the subject level rather than by treatment (because the questions are asked regarding the face rather than the treatment sides), for the 	

FACE-Q Rasch transformed score (0-100), which is converted from the sum score (range 5-20) across 5 items (symmetric, smooth, attractive, contour, and fullness), with each item scored on an ordinal scale from 1 to 4 (very dissatisfied, dissatisfied, satisfied, very satisfied); the FACE-Q Rasch score will be summarized for baseline and change from baseline to month 1 (primary measurement time)

[figure not shown]
Safety Assessments

- AEs, separately for AEs at cheeks, not at cheeks and combined
- Procedural Pain, based on subject assessment on an 11-point scale,
 response distribution by treatment, and paired treatment comparison

of each subject's difference score (-10 to +10)

• Injection Site Responses (ISR), based on subject's 30-day diary, overall and for each of 10 categories (redness, pain after injection, tenderness to touch, firmness, swelling, lumps/bumps, bruising, itching, discoloration and other), response distribution by treatment, separately for presence, severity (none, mild, moderate, severe), number of ISR days (none, 1-3, 4-7, 8-14 and 15 or more), and total duration (none, 1-3, 4-7, 8-14 and 15 or more days)

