5.1.4.2 Adverse Events

The following AE terms are defined:

Table 5-19 AE Terms

Term	Description
Treatment-	An AE that initially occurs or increases in severity on or after the treatment start date.
emergent AE	
(TEAE)	
Treatment-	A TEAE that is related to study treatment in the judgment of the investigator.
related TEAE	
(TR-TEAE)	

AEs, encompassing abnormalities and surgeries reported as occurring after the Screening Visit, will be coded using MedDRA version 20.0 or newer. A listing of all TEAEs will be presented. Also, unique subjects reporting AEs as well as number of events in the following AE categories will be summarized by treatment group and in total for the Safety Population as follows (ie, AEs at cheeks, AEs not at cheeks and all AEs combined). The overall summary tables of AE categories and the summary tables for TEAEs and TR-TEAEs that are grouped by SOC, PT and severity will be included within a CSR-appendix set of tables. The other AE summary tables listed will be generated within a supplemental set of tables.

Table 5-20 AE Summaries

Endpoint	Description	Timing	Methodology
Overall summary	Overall summary only for the following categories:	Treatment	Categorical counts
	 Treatment-emergent AEs (TEAEs) Treatment-related TEAEs All Serious AEs (SAE) 		
	Treatment-related SAE		
	Discontinued due to TEAEDeaths		
TEAEs	 by SOC and PT by SOC, PT, and severity (mild, moderate, severe) by SOC, PT, and duration (≤ 7 days, 8-14 days, 15-30 days, > 30 days) non-serious and occur ≥ 5%, by SOC and PT 	Treatment	Categorical counts
TR-TEAEs	by SOC and PTby SOC, PT, and severity	Treatment	Categorical counts
SAEs ¹	Overall summary and by PT	Treatment	Listing
AEs leading to discontinuation ¹	Overall summary and by PT	Treatment	Listing

¹ Subjects who report ≥ 1 AE in the AE category and all AEs for those subjects will be listed. SOCs will be sorted alphabetically; PTs will be sorted in descending frequency across treatments (cannula and needle).

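### The AE location field records side only for cheek events, so a one-sided facial or eye AE off the cheek has no recorded side for the cannula-versus-needle safety summary

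*Protocol*

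**What the plan says.** **What is randomised.** Each subject has one cheek treated by cannula and the other by needle. Protocol Synopsis, Study Design: "The side of treatment (ie, side of face for needle or cannula) will be randomized".

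**What is recorded.** Protocol Synopsis, Response Measures, lists ISRs, procedural pain and AEs as the safety measures and then states: "Location of these assessments will be noted as being on the right and/or left cheek or not applicable". The opening of Protocol Section 11 says AEs are "reported on an AE eCRF, including seriousness, severity, action taken and relationship to study treatment"; side and anatomical site are not among the items named.

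**What is analysed.** Protocol 8.3.4 makes the primary safety analysis a set of paired categories: the event on both sides, on the needle side alone, and "subjects who have the ISR (or AE) on the cannula side and not on the needle side". It adds a within-treatment percentage for each side.

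**How the SAP carries this out.** Table 4-1 lists "AEs, separately for AEs at cheeks, not at cheeks and combined". Section 5.1.4.2 asks for summaries by treatment group and in total, explained as "ie, AEs at cheeks, AEs not at cheeks and all AEs combined".

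**Which events are foreseen.** The list of known potential AEs in Protocol 11.1.1 includes vision changes after injection into a blood vessel. It also includes: "swelling or edema around the eye following an injection can result in a temporary decrease of vision".

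**The concern.** Product goes into both sides of the same face on the same day. Subject-level information cannot separate the devices: timing, exposure and relationship to study treatment are shared by both sides. Only the side of the event links it to cannula or needle.

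The stated location rule supplies a side for cheek events and for nothing else, whereas the analysis is written in terms of sides of the face. Swelling around one eye, or a visual change in one eye, is an event for which side is clinically meaningful and for which no side category is given. Vision changes are also among the gravest risks the protocol lists, and the study objective includes the safety of cannula injection. The named primary safety summary could therefore omit some of the one-sided events a reader would most want to see by device.

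The rule also leaves the boundary of the cheek open. Whoever records the event must choose between a cheek and not applicable, and that choice decides whether the event counts against a device.

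**Working it through.** The documents give no figure to reproduce on this point. The check traces the AE side from collection to table, then gives an illustration of scale.

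**1. Tracing the side**

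- *Needed:* Protocol 8.3.4 requires each AE to be placed on the cannula side, the needle side or both.
- *Device by side is known:* the randomisation assigns it, and Protocol 10.1.3 has kit numbers recorded so that treatment as given can be told from treatment as randomised.
- *Event by side is known only on the cheek:* the Synopsis categories are right cheek, left cheek, both, or not applicable.
- *Relationship does not recover it:* Protocol 11.1.8 relates the AE to the device or the treatment procedure, and SAP Table 5-19 relates it to study treatment. Neither separates cannula from needle in a subject who had both.
- *Source records do not require it:* Protocol 12.4.1 asks only for the occurrence and status of AEs.
- *The SAP has no assignment rule:* its instruction to summarise by treatment group cannot be carried out for a not-at-cheeks AE from a field that holds no side.

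Example: a subject treated by cannula on the left develops swelling around the left eye, recorded as not applicable. The subject is counted under AEs not at cheeks and in the combined table, but the recorded location provides no basis for the cannula-only category or the cannula-side percentage. Another site could record the same event as left cheek, and it would then count.

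**2. Scale**

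Inputs: n = 60 treated subjects (Protocol 5.1). The event counts and rates are assumptions. Affected subjects are taken to have no other AE that already places them in a side category. Intervals are exact Clopper-Pearson 95%; the limits for x events are the 2.5% quantile of Beta(x, n − x + 1) and the 97.5% quantile of Beta(x + 1, n − x), with lower limit 0 when x = 0.

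| One-sided off-cheek events, all on cannula side (assumed) | Cannula-only if given a side | Cannula-only if coded not applicable |
|---|---|---|
| 1 | 1/60 = 1.7% (0.04 to 8.9%) | 0/60 = 0% (0 to 6.0%) |
| 3 | 3/60 = 5.0% (1.0 to 13.9%) | 0/60 = 0% (0 to 6.0%) |

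The chance that at least one such subject occurs is 1 − (1 − p)^60:

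- p = 1%: 1 − 0.99^60 = 45%
- p = 2%: 1 − 0.98^60 = 70%
- p = 5%: 1 − 0.95^60 = 95%

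**3. Direction of the effect on the difference**

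Let a and b be the subjects with cannula-only and needle-only cheek AEs, and u and v the further subjects with one-sided off-cheek AEs on the cannula and needle sides. With off-cheek events omitted, the reported difference is (a − b)/60; with sides assigned it is (a + u − b − v)/60. The error is −(u − v)/60.

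- a = 4, b = 2, u = 1, v = 0: reported 2/60 = 3.3 points, with sides 3/60 = 5.0 points. The gap is understated.
- a = 2, b = 4, u = 1, v = 0: reported −2/60 = −3.3 points, with sides −1/60 = −1.7 points. The gap is overstated.

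Per-side rates can only fall through omission; the difference can move either way.

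**The case against.** **The location sentence is a synopsis line, not the data-capture specification.** The AE eCRF is not shown, the items named in Section 11 are introduced as inclusions rather than a closed list, and the visit procedures and parts of the statistical text are redacted. This stands as a limit: a separate side item cannot be excluded, and the fix is conditional on that. It does not supply the missing SAP rule assigning a non-cheek AE to a device.

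**The analysis says side, not cheek.** On that wording a left eye-area AE in a cannula-left subject is already on the cannula side. This is a fair reading of the intent. It also shows the mismatch: the analysis needs a side of face, and the stated field gives only a side of cheek.

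**Events next to the cheek may be recorded as cheek.** The MFVDS description in Protocol 7.1.1 includes tear troughs and nasojugal folds, so swelling below the eye could reasonably be coded there. Swelling and bruising are also in the 30-day ISR diary, which the SAP analyses by cannula and needle. Both points reduce the number of events affected. But no written rule secures the coding, and the treating investigator, who records AEs, knows which device was used on each side (Protocol 4.3.3). Vision changes are not among the symptoms the diary names.

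**The analyses are descriptive and the gravest events are described as rare.** This is correct. No test, error rate or sample size depends on the point, and with a single event the two intervals overlap heavily.

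**Stronger readings to avoid.** A reader might infer that these events vanish from safety reporting or are handled like an unrelated illness. They do not and are not: they remain in the not-at-cheeks and combined summaries, in the treatment-related tables if judged related, and in the listing of all TEAEs; serious events also require a written case history (Protocol 11.4). A reader might also take skin necrosis as an off-cheek example, but Protocol 11.1.1 gives it no site and it could occur on the treated cheek. The eye-area events carry the argument alone.

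**Conclusion.** The point holds, limited to the cannula-versus-needle comparison of AEs. The visible text gives a one-sided off-cheek AE no side, while the primary safety summary needs one. Such an event can drop out of the per-side percentages or be coded to a cheek inconsistently between sites.

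To the extent that events are coded not applicable, per-side rates are understated. It is tempting to add that the plan understates the difference between devices; the documents do not support that, because the error depends on how the omitted events split between sides and may have either sign.

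The size is unknown. Under the one-event assumption the cannula-only figure changes from 1.7% to 0% of 60 subjects. The conclusion assumes that the AE eCRF has no separate laterality item and that no redacted text assigns these events to a side. It is a worthwhile, inexpensive improvement to the trial's own within-subject safety question; it does not touch the primary effectiveness analysis.

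**What to change.** First check the AE eCRF. If it does not already hold the information:

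1. Record side of face for each AE (right, left, both, midline, not lateralised) as one item, and at cheek yes/no as a second. Amend the Synopsis sentence to match.
2. State in Protocol 8.3.4 and SAP Table 5-20 that every lateralised facial or ocular AE is assigned to the device actually used on that side, and show the cheek-only count as a subset. Align the AE entry in SAP Table 4-1.

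If the eCRF already records side, only step 2 and the matching wording are needed.

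The cost is at most one extra eCRF item and short text changes. No visit, procedure, sample size or error rate is affected. The downside is that reported per-side AE rates may rise slightly.
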